5.0 Study Design and Procedures

5.1 Study Design

Aims 1 & 2, combined, consist of a case-control study that will be completed over two visits lasting approximately 3-4 hours each, including: medical and psychological assessments, neurocognitive testing, and EEG/event-related potentials (ERP) procedures. Visits one and two may be completed up to three months apart. Following completion of Aim 1 and 2 studies, subjects and their guardians may be asked to participate in Aim 3.

Aim 3 (Intervention) consists of a two-visit, randomized controlled, crossover acute perturbation study to study the effect of AAE or sham stimulation on 1) the sensory auditory chirp (ITC and asynchronous gamma) and Passive SL Task (word learning ITC) and 2) in sufficiently cooperative participants, reaction time responses of an exploratory Active SL Task (word learning). AAE will be performed in two visits as a double-blind, sham-controlled crossover study such that each participant will receive AAE and sham in random order. For Aim 3, we estimate two 4-hour visits separated by at least a 1-week washout.

FX ENTRAIN Studies flow:

5.2 Procedures

The number of research visits for each subject may vary depending on subject age/functioning, tolerability of procedures, and family schedule. The research team will work to always fit the needs of

the subject/family. In line with this, subjects, caregivers, or parents may be given the option to complete appropriate surveys or questionnaires electronically through Redcap, over phone/video call with a member of the study team, or from home and mailed back to the research team. We may not administer all of the measures, assessments, or procedures, listed below. Measures administered will be at the discretion of the PI. If any data is unable to be collected, this will not be considered a protocol violation, but will be noted in the study chart. When applicable, assessments and measures previously collected from related, linked studies conducted by the Neurobehavioral Research Team and associated PIs can be transcribed and used for this study to reduce patient burden and the possibility of test-retest effects. Clinical data may include, but is not limited to, previous behavioral, neuropsychological, or other testing, and the results of any pertinent laboratory tests including previously conducted genetic chromosomal or microarray testing, vital signs, medication history, imaging history, CBC, metabolic panels, lipid panel, and other blood testing.

Standardized Measures and Assessments

Participants may complete the following:

[figure not shown]
1. **Brief medical history and physical exam** to determine any exclusion criteria and medication. Medication history will contain medication details including duration taking the medication, time of last dose, history (with start and stop dates) of discontinued medications, and any non-pharmaceutical treatments such as herbals or complementary medications. Physical exam may include height, weight, head circumference, vitals and CNS data.
2. **Hearing and vision tests** to assess adequate hearing threshold using conventional threshold measurements from 0.25 to 8 kHz with simple behavioral responses, and vision tests to confirm corrected far visual acuity of less than 20/40.
3. **Social Communication Questionnaire (SCQ)⁶⁷** which is a screener for autism spectrum disorder (ASD). TDC controls must score ≤ 8 to be included in the study and ASD controls must score < 15 to be included in the study.
4. **Autism Diagnostic Observation Schedule-2 (ADOS)⁶⁸** will be completed to assess for comorbid ASD in the FXS cohort, and to confirm ASD diagnosis in the ASD cohort. All ASD subjects and only FXS subjects scoring ≥ 12 on SCQ will complete the ADOS.
5. **Mini International Neuropsychiatric Interview Kid (MINI-KID)⁶⁹**: Structural diagnostic interview to assess call co-occurring disorders in all subjects. The standard MINI Kid assesses the 30 most common and clinically relevant disorders or disorder subtypes in pediatric mental health.
6. **Stanford Binet IQ Scale-5th Ed (SB-5)⁷⁰**. to provide a Full Scale, Verbal, and Nonverbal I.Q.
7. **Vineland Adaptive Behavioral Scales- Third Edition⁷¹**, to assess adaptive skills.
8. **Expressive Language Sampling (ELS)**, conversation, and narrative¹⁹ to assess naturalistic language abilities and heavily used in FXS.
9. **Clinical Evaluation of Language Fundamentals (CELF-5)⁷²**: Comprehensive evaluation of language abilities to determine the level or levels of language (e.g., semantics, morphology, syntax, and pragmatics).
10. **Parent-report measures** of psychological functioning: Aberrant Behavioral Checklist (ABC)⁷³; Anxiety, Depression, and Mood Scale (ADAMS)⁷⁴; Sensory Profile⁷⁵; Social Responsiveness Scale (SRS-II)⁷⁶; Repetitive Behavior Scale-Revised (RBS-R)⁷⁷; Pediatric Anxiety Rating Scale (PARS)⁷⁸; Pediatric Quality of Life (PQL)⁷⁹.
11. **NIH Cognitive Toolbox⁸⁰** for neurocognitive and neuropsychological skills.

Table 1: Detailed list of medical and standardized study assessments by cohort

Assessment	FXS	TDC	ASD	Remote Administration	Online Survey
Medical assessment (history, concomitant medication evaluation)	X	X	X	X	
Physical (height, weight, head circumference, vitals, CNS data)	X	X	X		
Hearing and vision screener	X	X	X		
Social Communication Questionnaire (SCQ)	X	X	X	X	X
Autism Diagnostic Observation Schedule (ADOS)	X*		X		
Mini International Neuropsychiatric Interview Kid (MINI-KID)	X	X	X	X	
Stanford-Binet Intelligence Scale, 5th Edition	X	X	X		
Vineland Adaptive Behavior Scale 3rd Edition	X	X	X	X	
Clinical Evaluation of Language Fundamentals (CELF-5)	X	X	X		
Expressive Language Sampling (ELS)	X	X	X		
Aberrant Behavior Checklist (ABC)	X	X	X	X	X
Anxiety, Depression, and Mood Scale (ADAMS)	X	X	X	X	X
Sensory Profile	X	X	X	X	X
Social Responsiveness Scale (SRS-II)	X	X	X	X	X
Repetitive Behavior Scale-Revised (RBS-R)	X	X	X	X	X
Pediatric Anxiety Rating Scale (PARS)	X	X	X	X	X
Pediatric Quality of Life	X	X	X	X	X
NIH Cognitive Toolbox	X	X	X		

* Only administered to FXS subjects with SCQ score ≥ 12

Detailed schedule of procedures by aim/visit

Neurophysiology Tasks

Table 2: Schedule of neurophysiology and neurocognitive procedures

Aim 1 (Visit 1): Sensory Auditory Studies	Aim 2 (Visit 2): Cognitive Studies	Aim 3 (Visits 3 & 4): Closed-Loop Neural Perturbation Studies
Resting State EEG	Resting State EEG	Resting State EEG
Sensory Auditory Chirp	Passive SL Task	AAE ¹ Baseline
Auditory Steady State	Active SL Task	Sensory Auditory Chirp
AAE ¹ Baseline	AAE ¹ Baseline	Passive SL Task
		Active SL Task

¹AAE, Alpha Auditory Entrainment Paradigm

EEG/ERP Procedures

EEG/ERP may be used to assess the electrophysiologic correlates of exposure to sensory stimuli (i.e. auditory/, visual, tactile) and/or during behavioral computerized testing. Recordings are acquired using 32 up to 256-channel cap (HydroCel Geodesic Sensor Net) with an amplifier. Data are recorded at a sampling rate of 1000 Hz with saline-based electrodes. Acoustic stimuli are generated and presented using MATLAB (MathWorks, Natick, MA) and synchronized with a pulse to mark the onset of each stimulus. Video may be recorded to accurately identify non-brain artifact contamination of the recording. In order to facilitate accurate EEG electrode locations on the scalp during analysis any subject that receives an EEG may be photographed to determine electrode positions during recording; this may include a 5-10 minute procedure in which the EEG net and electrode positions are captured using photogrammetry software and a stereoscopic camera. Data will be used to generate a numerical coordinates file. All EEG collection will be completed by trained research staff members. Our team developed systematic behavioral preparation including social stories, visual schedules, and demo nets/parent training to optimize data collection. In our experience, >95% of study eligible individuals with FXS provide usable EEG data following our study protocols. To maintain cooperation with study procedures, resting and sensory EEG is performed while watching a standardized silent cartoon. Behavioral tasks will use response button boxes.

1. **Resting state EEG:** Continuous data will be recorded for 5-7 minutes.
2. **Sensory Auditory Chirp:** "Chirp" stimuli will be delivered through headphones/speakers with a 1000-Hz carrier tone amplitude modulated (AM) by a chirp sinusoid linearly increasing in frequency from 0–100 Hz over 2000 ms. One-to two-hundred stimuli will be separated by a 1.5-2 sec inter-trial interval, for 7.5-12.5 minutes of testing.
3. **Sensory Auditory Steady State:** As an exploratory outcome, we may test stability of synchronization at alpha (10 Hz) frequency and its relation alpha power phase. Stimuli will consist of white noise amplitude modulated by a sinusoid for 3 sec at 10 Hz. Fifty trials at each frequency (100 trials total) will be randomly presented and separated by a 1.5-2 sec inter-trial interval, for 8.3 minutes of testing.
4. **Alpha Auditory Entrainment (AAE) Baseline:** The AAE was generated in MATLAB 2019b with a 500 Hz sine carrier wave. We had five total conditions including silence (no stimulus), sham (500 Hz both ears), and linearly increasing alpha frequencies of 7 Hz (507 Hz in right ear), 9 Hz (509 Hz in right ear), 11 Hz (511 Hz in right ear), 13 Hz (513 Hz in right ear). The total stimulation length is twelve minutes with one minute of stimulation of each frequency in pseudorandom order.
5. **Dynamic AAE during closed-loop perturbation:** The requested frequency differential will be generated by a custom function in MATLAB to deliver AAE in the requested .5 Hz step. This stimulus will last for 60 seconds until the next iterative feedback. Combining AAE with paradigm: The AAE stimulus will be played back at background noise level alongside either the sensory auditory chirp or SL tasks. There is considerable literature on the combination of entrainment beats with other auditory stimuli (speech, music) maintaining the physiological response⁸¹⁻⁸³.
6. **Sham AAE:** The sham stimulus was generated in MATLAB with a 500 Hz sine carrier tone. The sham AAE condition will mimic the closed-loop AAE condition detailed above, however only the

carrier stimulus (500 Hz) is mixed with the paradigm audio during sensory auditory chirp or SL tasks.

Eye Tracking

[figure not shown]
Participants may be monitored or asked to make specific eye/eyelid movements. Behavioral and emotional tasks may be used in conjunction to monitor eye movements. This task involves the subject to look at a sequence of varying emotional faces and social sequences. The resulting ocular movements may be recorded using a Tobii Eye Tracker (Tobii Technology AB, Danderyd Sweden) or similar scanner-compatible technology.

Statistical Learning Tasks

Assessment of SL includes a 1) Passive SL Task and 2) Active SL Task. This approach allows us to capture data on all participants regardless of adaptive functioning. The Passive SL Task uses an EEG-based measure of neural entrainment involving ITC^{31, 53} to calculate Word Learning Index (WLI). The Active SL Task based measure uses reaction time to estimate a behavioral measure of SL, the Behavioral Learning Effect BLE³². The tasks may be altered (e.g., speed reduced, additional instruction or practice given) to increase feasibility for participants.

Procedure Overview (all SL tasks)

Participants will be seated in front of a computer monitor with headphones compatible with EEG cap. If a subject is not able to tolerate headphones, alternative methods like speakers may be used instead. To facilitate cooperation and reduce motion artifact, standardized, silent non-social videos will be played during the task. Stimuli (see Fig. 1): Twelve syllables are combined to make four, three-syllable pseudowords. This miniature synthetic language resembles natural language as (1) transitional probabilities are higher for neighboring syllables within words than across word boundaries and 2) a given syllable may be present in more than one word. For example, a transitional probability of 1.0 for

a syllable pair such as "vinay" indicates that every "vi" in the stream was followed by "nay." SL occurs as the brain "discovers" hidden words in the speech stream by becoming sensitive to these linguistic patterns through repeated exposure.

Passive SL Task: Each participant will be presented with both a structured and random stream of syllables. The structured stream will consist of the four generated words, concatenated in pseudorandom order without any pauses or acoustic cues between words (e.g., *vinayfeetidomoo...*). Each word will be presented 200 times, for 800 total word presentations. Order will be constrained to avoid successive syllable and word repeats. The random stream contains the same total number of syllables, which are ordered pseudorandomly to avoid syllable repetitions but will otherwise not follow

any hidden structure. Words will be presented at a rate of 1.1 per a second (thus, syllable rate is 3.3 Hz), resulting in 10 minutes of each structured and random continuous stimuli. As previously published, the expected outcome of this study is an increase in EEG phase-locking at 1.1 Hz over the exposure period—present in the structured condition only—indicative of gradual word discovery and successful word segmentation resulting from statistical learning.

Word-learning Index (WLI) for Passive SL: WLI is the primary EEG outcome measure for the exposure task and, similar to our sensory studies, is based on intertrial phase coherence (ITC). As the participant "learns" the four words in the structured stream (i.e., uses statistical probabilities across neighboring syllables to segregate the speech stream), their EEG typically shows increased phase-locking (increased ITC) at the word presentation rate (1.1 Hz) and decreased phase-locking at the syllable presentation rate (3.3 Hz). Thus, patterns of EEG phase-locking, corresponding to a shift in processing from raw syllable units to cohesive words, reflect gradual statistical learning in the brain. The effect can be quantified by creating a ratio of the ITC for words versus syllables, as follows:

$$WLI = \text{Intertrial Coherence}_{\text{word rate}} / \text{Intertrial Coherence}_{\text{syllable rate}}$$

A higher WLI indicates a relatively stronger response to tri-syllabic nonwords compared to raw syllables, reflecting stronger word segmentation due to statistical learning. The WLI predicts subsequent performance on behavioral tests of statistical learning and increases over time in the structured condition only, and not in the random condition³¹.

Active SL Task (Exploratory): Following the exposure task, each participant may attempt to perform a reaction-time based task that provides a behavioral index of SL. Participants will be instructed to press a button when they hear a given target syllable (e.g., "moo"). Prior to the main task, the participant may complete 10 practice attempts on non-experimental syllables to assess feasibility. The four words from the exposure task will then be presented a total of 20-45 times per word across a total of five, one-minute blocks, each corresponding to a separate target syllable. Within each one-minute block, each of the six words will be repeated 4-9 times. A visual reminder of the target (e.g., a picture of a Cow for "moo") will be displayed for the entirety of the block. Targets presented within later positions within a nonsense word, (i.e., those syllables that are more predictable) elicit faster reaction times than less predictable, word initial syllables, providing a reaction-time based measure of statistical learning. Thus, the Behavioral Learning effect can be quantified as follows:

$$BLE \text{ (in ms)} = (\text{Reaction time}_{\text{target syllable position 1}}) - (\text{Reaction time}_{\text{target syllable position 3}})$$

Larger BLE values indicate greater proportional facilitation to predictable words in the stream, indicative of stronger SL at the individual level. Group comparisons can be facilitated by dividing BLE by the Reaction time_{target syllable position 1} to normalize to an individual's baseline reaction time. Larger BLE values indicate greater proportional facilitation to predictable words in the stream, indicative of stronger SL at the individual level.

Interventional Agent: Alpha Auditory (Neural) Entrainment

Randomized, sham-controlled acute neural perturbation studies will test the hypothesis that enhancing alpha oscillations in FXS will enhance thalamocortical drive in FXS and normalize observed neuro-oscillatory alterations in sensory and cognitive paradigms. As this is a highly novel approach, we have attempted to reduce the complexity of the protocol to be feasible in youth and simplify interpretation for future chronic dosing studies.

Procedure Overview

Three segments (approximately 15 minutes each) will be conducted to 1) identify the baseline AAE, 2) conduct closed-loop perturbation sensory studies, and 3) conduct closed-loop perturbation SL studies. Similar to Aim 1 and 2 studies, subjects will be seated comfortably and allowed to watch silent, non-social videos during setup, segment 1, and the passive portion of segment 2 to facilitate cooperation and reduce movement artifact. Following the first segment, the subject will be offered a 5 to 10-minute break.

Baseline AAE (Segment 1): To avoid extensive "frequency finding" during the closed-loop segments we have opted to perform a linear increasing auditory entrainment paradigm to identify an optimal starting frequency. We will record 3 to 5 minutes of resting state EEG prior to the AAE baseline paradigm. The brain computer interface (BCI) will provide real-time detection of peak-power frequency and magnitude of the target frequency range at each frequency step and will be recorded with subject data. Following completion of the baseline AAE paradigm for each subject, the investigator(s) will evaluate output curves and determine optimal starting frequency. Segment 1 is performed during AAE or sham treatment conditions.

Closed-loop segments 2 and 3: Paradigm procedures for both sensory auditory chirp and SL paradigm will be identical to Aims 1 and 2, with the addition of the AAE stimulus (either active or sham) to the paradigm audio. As the SL Tasks syllables can be varied, the subjects will learn a new "miniature" language on each visit. In the closed loop condition, prior to starting paradigm sixty seconds of the selected baseline AAE will be delivered via earphones before the start of the paradigm to capture sufficient data for feature feedback. Following initiation of the paradigm, every 60 seconds a moving average of peak power frequency will be broadcast via LSL to MATLAB for adjustment of entrainment frequency. If the peak power frequency is less than the target frequency entrainment stimulation will advance by .5 Hz. If the peak power frequency is higher than the target frequency, the entrainment stimulus will decrease by .5 Hz. If the peak power frequency is within the target, no change in frequency will be performed. As in Aim 2, all subjects will receive the SL exposure task, however, subject feasibility will be assessed for completion of the SL performance task. Following completion of paradigm, subjects will be allowed to watch a video of their choice (with sound) as the EEG cap is removed to facilitate cooperation and serve as a reward.

5.4 Protection Against Risks (all aims)

All experimental procedures will be carried out in a setting and among staff who are carefully trained and experienced in working with individuals with developmental disabilities including FXS and ASD. All human research procedures take place on the clinical campus of CCHMC. In addition to the on-site presence of an attending physician who is PALS certified, the clinical resources of CCHMC will be available in the case of an adverse event which includes access to AED equipment and the Emergency Department. See **Risks to Subjects** section for detailed precautions against risks.

6.0 Sharing of Results with Subjects

Findings from assessments will be made available to agents of the participants (parents, schools, treating psychologists, physicians) only with the expressed, written consent of the parents/guardians and if appropriate for the study participant.

The study investigator team is joined by a pediatric neurologist ([name]) with expertise in clinical EEG and brain stimulation and extensive collaboration with the P.I. on pediatric TMS studies⁸⁴⁻⁸⁹. Since ASD patients have a higher risk for epilepsy than the general population, the neurologist's role will be to review all research resting-state EEGs for abnormalities, including evidence of seizure activity. If any abnormalities are found, these findings' clinical relevance and urgency and the need for a neurological exam will be discussed with the principal investigator. The findings will be directly discussed with the family with appropriate clinical referral. In addition, any features of clinical significance within the EEG recordings will be considered in subgroup and co-variate analysis.

7.0 Study Timelines

Individual subjects' duration of participation in this study is estimated to be approximately 16 hours over the course of up to two years, with up to three months of separation allowed between visits 1 and 2 (descriptive study), and 3 and 4 (clinical trial), respectively. It is expected that participants' duration of participation will be significantly shorter than is stated above, however, considering many FXS families travel great distances to be seen in our lab clinically, high flexibility in scheduling is imperative for ensuring equal opportunity to those who wish to participate in research.

We plan to enroll all study subjects by end of year 4 and estimate the primary analyses will be completed by end of year 5.

8.0 Inclusion and Exclusion Criteria

Inclusion Criteria (all aims):	FXS	ASD	TDC
Aged 5-15 years, inclusive	X	X	X
Patient has full FMR1 mutation confirmed by genetic testing	X		
Have no known genetic mutation		X	
Have documentation of ASD diagnosis		X	
Score ≤ 15 on SCQ screen		X	

Be in good health per investigator		X	X
Patient has met normal developmental milestones			X
Patient has no family history of heritable neuropsychiatric disorders			X
Patient has an IQ greater than 85 on the Stanford-Binet			X
Score ≤8 on an SCQ screen			X

Exclusion Criteria (all aims):	FXS	ASD	TDC
Patient has auditory or visual impairments that cannot be corrected	X	X	X
History of substance abuse or dependence within the past 6 months	X	X	X

Vulnerable Populations

- Inclusion of women and minorities: We will include males and females in numbers consistent with the distribution expected in the clinic populations. We will not exclude any participant based on race or ethnicity. The distribution of minorities will be consistent with the distribution expected in Cincinnati.
- Inclusion of children: A central aim of the proposed research is to evaluate the underlying mechanisms responsible for brain development in children with FXS. This can only be done by studying affected individuals in that age group. The minimum age of 5 was chosen because of the level of cooperation required to complete procedures, and the upper age limit of 15 was chosen because of common age-related changes in behavior and brain function beyond that age.
- Persons with Cognitive Impairment or other limited decision-making capacity: To be inclusive and most generalizable in our study findings, and because some elements of our protocol can be completed with minimal cognitive requirements, such as event-related potential (ERP) monitoring of cortical responses to tones, we will recruit any study-eligible patient with Fragile X Syndrome regardless of level of cognitive disability into as many study components as they can complete. We will recruit all FXS patients who we believe can complete study procedures.

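### The two SCQ limits for ASD controls disagree at a score of 15, and both are maximums, so high-scoring children with ASD are barred and the direction appears reversed

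*Combined protocol and SAP*

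**What the plan says.** The SCQ rule for the ASD cohort appears twice. Section 5.2, item 3 (SCQ), says "ASD controls must score < 15 to be included in the study". The inclusion table in Section 8.0, which covers all aims, has "Score ≤ 15 on SCQ screen" marked in the ASD column only.

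The protocol's other uses of the scale are:

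- Section 5.2, item 3, describes the SCQ as a screening tool for ASD and sets the limit for typically developing controls: "TDC controls must score ≤ 8 to be included in the study". Section 8.0 gives the same limit of 8.
- Section 5.2, item 4: "All ASD subjects and only FXS subjects scoring ≥ 12 on SCQ will complete the ADOS". The footnote to Table 1 repeats the trigger of 12 for FXS subjects.
- For the ASD group, the ADOS is there "to confirm ASD diagnosis in the ASD cohort".
- Section 8.0 lists "Have documentation of ASD diagnosis" as a separate inclusion criterion for ASD controls.

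No section gives a minimum SCQ score for the ASD cohort or a reason for a maximum.

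**The concern.** There are two problems. The first is a plain contradiction: the sections use different inequality signs and disagree about a score of 15. The second is direction. A screener on which high scores suggest ASD has been given an upper limit, and no lower one, in the cohort that is meant to have ASD.

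At stake is who the ASD comparator represents. Section 14.0 (Data Analysis) names FXS vs ASD among the primary comparisons for Aims 1A and 2, makes it one of two models in Aim 3, and uses it to argue that group differences are not due to intellectual ability and genetic liability alone. If staff apply the limit as printed, children with documented ASD and high SCQ scores are left out, and the comparison is with a group selected for lower scores. Section 9.0 describes these controls only as matched and idiopathic, and Section 10.0 recruits from inpatient and outpatient developmental-disability services. Neither mentions an SCQ limit, so a reader could take the result to cover a broader ASD population than the one enrolled.

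**Working it through.** No published figure in the plan depends on this rule, so there is nothing to reproduce. The check applies each rule to the scores at its boundary, assuming whole-number scoring.

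| SCQ score | TDC rule (≤ 8; Sections 5.2 and 8.0) | ASD rule, Section 5.2 (< 15) | ASD rule, Section 8.0 (≤ 15) |
|---|---|---|---|
| 8 | eligible | eligible | eligible |
| 12 | not eligible | eligible | eligible |
| 14 | not eligible | eligible | eligible |
| 15 | not eligible | **not eligible** | **eligible** |
| 16 | not eligible | not eligible | not eligible |

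1. **Conflict.** The ASD rules differ at one score only: 15 < 15 is false and 15 ≤ 15 is true.
2. **Overlap.** Any score ≤ 8 is also < 15 and ≤ 15. The TDC range therefore lies wholly inside the ASD range under either wording. With scores starting at 0, that is all nine values from 0 to 8.
3. **Exclusion.** Every score of 16 or more fails both ASD rules. Of the scores at or above the protocol's own ADOS trigger of 12, only 12 to 14 (Section 5.2) or 12 to 15 (Section 8.0) can enter the ASD cohort.
4. **Direction.** Three features imply that higher means more autism-like: the SCQ is called an ASD screener, TDC are capped at 8, and FXS subjects at 12 or above go on to the ADOS. A maximum for the ASD cohort runs against all three. For illustration, a minimum at the same number (≥ 15 or > 15) would share no score with the TDC range.
5. **No rescue by other criteria.** The documented diagnosis and the ADOS are additional to the SCQ line. They cannot admit a child who fails it.

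**Reach.** Section 14.0 gives PPF (Aim 1A) and WLI (Aim 2) as primary responses, and 40 Hz ITC and WLI for Aim 3. Each is compared FXS vs TDC and FXS vs ASD:

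- Aim 1A: 1 × 2 = 2
- Aim 2: 1 × 2 = 2
- Aim 3: 2 × 2 = 4

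The total is 8 fits, of which 1 + 1 + 2 = 4 use the ASD group. The ASD target is 40 (case-control) + 20 (Aim 3) = 60. These counts show where the rule reaches, not the size of any bias. They leave out the other Aim 1 outcomes that Section 4.0 lists as primary.

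**The case against.** The strongest reply is that only one score is proven to be in conflict. The reversed direction is an inference. If staff already apply a minimum, nobody is wrongly excluded and the correction is editorial. That is right as far as it goes. But the documents do not show what staff do, and anyone following either section as printed must turn away a child with ASD who scores 16 or more.

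A second reply is that the overlap with TDC scores does no harm. ASD controls need a documented diagnosis and complete an ADOS, while TDC must meet separate criteria on milestones, family history and IQ. This stands: a shared SCQ score does not by itself put a child without ASD into the ASD group. The overlap shows only that the limit does not separate the two cohorts. The harm lies at the upper end.

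Third, Sections 9.0 and 10.0 need not repeat every criterion, and Section 8.0 states the limit openly. This weakens the worry about misreading but does not remove it, since an unexplained ceiling is easily missed when results are summarised.

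Fourth, the FXS vs ASD model adjusts for SRS score, psychiatric diagnoses and medication as well as non-verbal IQ. Adjustment helps with measured differences among enrolled children but cannot restore those never enrolled.

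Two other explanations fail. A PDF reading error is unlikely, because two sections carry different symbols pointing the same way and the opposite sign prints correctly elsewhere in Section 5.2. The investigator's discretion in Section 5.2 over which measures to administer does not settle which SCQ rule governs eligibility.

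**Conclusion.** The concern holds and should be fixed. It is certain that the sections conflict at a score of 15, that both rules are maximums, and that scores of 16 or more are barred from the ASD cohort in all aims. That the direction is reversed is an inference held with moderate confidence. It rests on the protocol's own use of the scale, and no section states the intent.

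If the rule is applied as written, the severity range and representativeness of the ASD comparator are narrowed in the FXS vs ASD models of Aims 1A, 2 and 3. The number of children affected and any bias cannot be calculated without an SCQ distribution.

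The rule does not touch FXS vs TDC, to which Section 14.0 gives priority, the AAE vs sham contrast within FXS, or the stated power. The non-verbal IQ covariate and the IQ matching described in Section 9.0 also remain in the plan, so FXS vs ASD can still address an explanation based on intellectual ability. Whether a ceiling would make IQ matching harder to achieve is unknown.

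**What to change.** Reconcile Section 5.2, item 3, and the Section 8.0 inclusion table to a single ASD criterion, stating its direction and the handling of a score of 15. The sponsor has three options:

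- write the rule as a minimum, at the cut-off the sponsor intended;
- remove the SCQ bound for ASD controls and rely on the documented diagnosis plus the ADOS that all of them already complete;
- keep a ceiling if it is truly intended, give the reason, and describe the ASD cohort as SCQ-restricted wherever FXS vs ASD is interpreted.

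If any ASD candidates have been screened, check the screening records for which rule was applied, and in particular whether anyone was turned away at 15 or above.

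The cost is two edited lines and, if screening has begun, that check. No procedures or sample size are added.
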